The Revised Photographic Wound Assessment Tool (RevPWAT) is an assessment tool based on the Bates-Jensen Wound Assessment Tool (formerly known as the Pressure Sore Status Tool) for assessments based on photographs of wounds rather than bedside assessments (Thompson, et al., 2013). This outcome measure has been chosen as it does not require the assessors to be at the bedside of the participants, thus blinding them from the allocated mattresses. Blinding assessors from allocated mattresses has been problematic for many of the studies in the literature as the mattresses have visible differences. Thompson, et al. (2013) tested the RevPWAT for reliability and found a strong correlation between bedside assessments and assessments from photographs (intraclass correlation coefficient of 0.89). See Appendices A and B for the assessment tool and instructions on how to score it.

DELIVERY AND FREQUENCY: Photographs for this assessment tool will be taken by clinicians at each wound care session to measure the progression of wound healing and will be scored by assessors blinded to allocated treatment group.

Secondary - Subjective Factors of Pressure Mattresses

Research has shown that there is a strong correlation between non-use of assistive technology and user dissatisfaction, with some of the factors relating to comfort and ease of use (Federici & Borsci, 2011). Regarding pressure mattresses, this means that equipment abandonment will be more likely if the client does not find the mattress comfortable or struggles with moving on it. These subjective measures are considered just as important as wound healing time and so will be measured through surveys provided approximately one week after mattress provision, utilising a Likert scale. The following factors will be included in the survey:

- participants' perceptions of the allocated mattress positives and negatives
- perceived change in sleep habits including:
 - time spent in bed
 - frequency of repositioning
 - sleep position
- comfort of the mattress, including changes in pain levels (see Pain Scale below)
- ease of transfers
- ease of use, including any troubleshooting they have needed to do to date

DELIVERY AND FREQUENCY: This survey will be completed at baseline and then again approximately 1-2 weeks after mattress provision. It will be completed by the participants and facilitated by the primary researcher.

Secondary - Pain Scale using 10-point Scale (Richards, 2015)

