Mattresses that have dual-functionality are excluded. This may be the ability to switch between static and alternating, such as Talley Quattro or Arjo Duo2; or mattresses that use combined static and alternating functionality, such as Curocell Cirrus or Talley Quattro Fusion. Although these mattresses may have clinical applicability in a community setting, their use during the study could confound results, particularly if they are not used as allocated, for example switched to alternating when the participant has been allocated to the static treatment group.

Cushions

To ensure that changes in pressure injuries are due to the mattress and not impacted by time spent sitting out of bed, all participants will be provided with the same air pressure cushion. Air cushions have been shown to have the lowest interface pressure, along with water cushions (Defloor & Grypdonck, 2000). As there are not many water cushions commercially available, an air cushion will be used (high profile ROHO cushion). These cushions are commonly prescribed for people at high risk of developing pressure injuries and so will be familiar to the treating clinicians should any trouble-shooting be required.

Wound Care

Wound care will be provided to the participants as per the current practice for Community Care Nursing, ACT Health. This includes the use of best-practice methods, such as Mepilex range as wound dressing with foam or cavity fillers as needed. Frequency of wound care days will vary depending on the stage of healing. Generally for Grade 2 wounds, wound care occurs every second day, reducing quickly to twice a week, then once per week. Once the wound reaches the stage of visits once per week the wound is considered almost healed as per the RevPWAT (score <2) and thus endpoint for the study.

Data Collection

Participants will be individually coded to prevent identification by assessors and by primary investigator when collecting survey data. Data will be kept in a limited-access folder on secure ACT Health servers behind ACT Health firewalls.

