Comparing wound healing times	Independent t-test (average healing time reactive surfaces vs average healing time active surfaces)			
Comparing number of new pressure injuries developed	Independent t-test (total number of new pressure injuries reactive surfaces vs total number of new pressure injuries active surfaces)			
Comparing number of pressure injuries not healed at 8 weeks	Independent t-test (number of pressure injuries not healed at 8 weeks for reactive surfaces vs active surfaces)			
Changes in Pain scores	2-way Mixed ANOVA – between group analysis to compare pre- and post-pain scores for each mattress type, independent group analysis to compare the mattress types			
Changes in time spent in bed	2-way Mixed ANOVA – between group analysis to compare pre- and post-time for each mattress type, independent group analysis to compare the mattress types			
Changes in frequency of repositioning	2-way Mixed ANOVA – between group analysis to compare pre- and post-frequencies for each mattress type, independent group analysis to compare the mattress types			

If the assumptions cannot be met, despite data transformation, then the relevant non-parametric tests will be completed (eg Mann-Whitney instead of Independent t-test).

Ethical Considerations

Ethics Approval

Ethics approval for this study will be sought from the ACT Health Human Research Ethics Committee and the University of Canberra Human Research Ethics Committee. As the design of the study reflects current practice, with all chosen mattresses being supplier-stated to be appropriate for Grade 2 pressure injuries, there will be minimal risk to participants for participating.

Data Management

During the data collection phase, data will be kept in restricted folders on ACT Health servers behind ACT Health firewalls so that all required parties will be able to access the data, negating the need for data to be emailed or transferred via USB. At the completion of the project the data will be de-identified and a copy provided to University of Canberra for archiving. This record is expected to be maintained for a minimum of seven years as per ACT Legislative requirements ("Health Records (Privacy and Access) Act 1997 (Republication No 27) (ACT)," 2016). Clinicians will continue to document in the clinical file as per current policy, including the allocated mattress.

Consent and cognitive impairment

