b) Provision of support surface will be based on availability.c) Mattress and cushion to be provided and set-up	Primary Researcher ELS Staff Primary Researcher OR ELS Staff
type and ROHO cushion b) Sales Representative to choose mattress from pre-determined list based on mattress type and storeroom availability c) Mattress and ROHO cushion to be provided and set-up	Primary Researcher Sales Representative Primary Researcher OR Sales Representative Primary Researcher
 mattress and cushion, including contact information 12. Wound Management: Wound Management as per standard practice with the following additions: Photograph to be taken as per study recommendations at every dressing change Review participant for changes in function, including skin check for new pressure injuries if new pressure injury has developed this should be photographed and referred to Wound Nurse Practitioner and Primary Researcher for review for ethical impact Repeat Waterlow weekly 	Community Nurses
13. Photograph Management: Photograph will be placed in ACT Health e-note template for photographs in a clinical file with unique identifier only (photograph enlarged for one photograph per page). Document to be saved in PATHFILE (Saved as: "Photograph [Unique identifier] — [date YYMMDD]"), where date is date photo was taken	Community Nurses
	Tissue Viability Nurses
 Data Entry Data from RevPWAT to be entered into data spreadsheet on a weekly basis by Research Team Data from hard-copy surveys will be entered into Qualtrics by Research Team as they are completed (to be entered within one week of survey) 	Primary Researcher Research Team/Admin Support Research Team/Admin Support Primary Researcher

Step	Who
 Participant Completion of study endpoints will be determined by one of the following: e one week following complete healing of the initial pressure injury as determined by the RevPWAT (ie at the point when Community Nursing would be leaving the dressing on for a week – PWAT score of 0 for all subscores except subscore 8, where a score of up to 2 can be permissable) e weeks following the provision of the mattress e removed from the allocated surface – for example by request, move areas, hospitalisation, death, significant deterioration of existing wounds (such as progression to a Grade 3 pressure injury or development of an unstageable pressure injury) 	Information only

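### Healing is dated only at care-driven dressing visits, but the named tests take that date as the healing time and give unhealed wounds no value

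*Protocol*

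**What the plan says.** The primary outcome is time to complete healing on the RevPWAT (Protocol, Outcome Measures). On how it is observed, that section says: "Photographs for this assessment tool will be taken by clinicians at each wound care session". The images are then "scored by assessors blinded to allocated treatment group".

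The Wound Care section fixes no study visit schedule: "Frequency of wound care days will vary depending on the stage of healing". It gives the usual pattern: "Generally for Grade 2 wounds, wound care occurs every second day, reducing quickly to twice a week, then once per week". It then ties the last step of that pattern to the endpoint: "Once the wound reaches the stage of visits once per week the wound is considered almost healed as per the RevPWAT", with a score below 2. Appendix A describes completion differently: one week after complete healing of the initial injury, with zero on every subscore except the eighth, which may be up to 2. It glosses this as "at the point when Community Nursing would be leaving the dressing on for a week".

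Treating clinicians are not blinded. The literature discussion says that this is impossible with visibly different mattresses, and Data Management has them record the allocated mattress in the clinical file.

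For the analysis, the Statistical Analysis table names "Independent t-test (average healing time reactive surfaces vs average healing time active surfaces" and allows Mann-Whitney if assumptions fail. A separate row counts injuries not healed at 8 weeks. The sample is 80 enrolled for at least 60 analysed, 30 per arm, without a power calculation or a standard deviation. The equivalence criterion refers to a pre-determined effect size but gives no value.

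**The concern.** True healing is known only to lie between two photographs. The recorded date is the first visit at which the wound is seen healed, so it is late by an amount that depends on the visit gap. Blinded scoring protects how each photograph is read, but not when it is taken. Neither named test uses the interval. Visit spacing is not among the confounding factors to be monitored or the listed audit items, so an imbalance between arms could go unnoticed.

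The second gap is more basic. A wound still open at 8 weeks, or last photographed before it healed, has no healing time to enter into a mean. The protocol does not say how such wounds enter the healing-time comparison. Mann-Whitney could place them at the highest rank, but this is not stated, and it would not suit participants who leave early.

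At stake are a false difference created by visit timing, and a true difference shrunk because the slowest wounds drop out. In a trial meant to show equivalence, the second is the more dangerous.

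**Working it through.** **Inputs from the protocol.** Visit gaps of 2 days, then twice a week (7/2 = 3.5 days), then 7 days (Wound Care); 30 per arm (Sample size); 8 weeks = 56 days (Statistical Analysis table). A median healing time of 20 days, reported for one reviewed trial in the evidence table, is used for scale only.

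**Assumed.** The protocol gives no SD. The range used is 5 to 20 days. Where a skewed distribution is needed, it is lognormal with log-SD 0.6.

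The plan has no figure of its own to reproduce on this point.

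**1. Detection delay.** For gap g and a random position within it, the mean delay is g/2 and its SD is g/√12.

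| Gap (days) | Mean delay (days) | SD of delay (days) |
|---|---|---|
| 2 | 1.00 | 0.58 |
| 3.5 | 1.75 | 1.01 |
| 7 | 3.50 | 2.02 |

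**2. False difference if the arms differ in spacing and true healing is identical.**
- 2 against 3.5 days: 1.75 − 1.00 = 0.75 day
- 3.5 against 7 days: 3.50 − 1.75 = 1.75 days
- 2 against 7 days: 3.50 − 1.00 = 2.5 days

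The last two need weekly visits before the healing photograph. A milder version of that case has one arm moving to weekly visits at day 14 and the other staying twice weekly (lognormal, median 20). It gives mean delays of about 3.0 and 1.7 days, a false difference of about 1.2 to 1.4 days depending on the exact visit grid.

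**3. Effect on the test.** Two-sided 5% rejection is Φ(−1.96 + δ/SE) + Φ(−1.96 − δ/SE). At the simulated SE of 4.08 days for the lognormal case:
- δ = 0.75: δ/SE = 0.184, rejection 5.4%
- δ = 1.41: δ/SE = 0.346, rejection 6.4%

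Simulation with gamma healing times (20,000 trials per setting, 30 per arm, no true difference):

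| Gaps compared (days) | Rejection, SD 5 | SD 10 | SD 20 |
|---|---|---|---|
| 2 vs 3.5 | 8.8% | 5.8% | 5.2% |
| 3.5 vs 7 | 25% | 9.9% | 6.9% |
| 2 vs 7 | 45% | 16.2% | 8.0% |

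**4. Equal spacing.** A common delay cancels from the difference in means. Simulated rejection stayed at 4.7% to 5.2%. When both arms followed the same stage-driven rule, a true difference of 4.97 days was observed as 4.82, and one of 4.94 as 4.94. The added noise is trivial. An SE of 4.08 implies SD = 4.08 × √15 = 15.8 days, and √(1 + 3.5²/(12 × 15.8²)) = 1.002. For 7-day gaps the factor is 1.008.

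**5. Wounds not healed by 56 days.** Assume lognormal healing with medians 20 and 28 days and log-SD 0.6. The full mean is median × e^0.18, so 23.9 and 33.5 days: a difference of 9.6. If unhealed wounds are dropped, the mean becomes (full mean) × Φ(z − 0.6)/Φ(z), with z = ln(56/median)/0.6.
- Median 20: z = 1.716; 23.94 × 0.868/0.957 = 21.7 days
- Median 28: z = 1.155; 33.52 × 0.711/0.876 = 27.2 days

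The difference falls to 5.5 days. The share dropped is 4.3% in one arm and 12.4% in the other.

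**6. Does the remedy work?** In 1,000 simulated trials of the step 2 scenario (weekly from day 14 in one arm), treating recorded dates as exact gave a false effect of 4.8% on the log scale. An interval-censored Weibull model gave 0.7% (Monte Carlo standard error 0.6%).

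**The case against.** The strongest case against is that spacing is standard care in both arms and follows healing. Nothing in the protocol suggests that nurses would space visits by mattress. This stands: the bias is conditional, and the protocol shows only that spacing is uncontrolled, in unblinded hands and unmonitored.

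A second objection concerns size. The Wound Care section makes the step to weekly visits the endpoint itself, so gaps before it are about 2 to 3.5 days. This also stands. A reader might infer from the 2-to-7-day range that false differences above a day are likely, but on that section's wording they cannot arise.

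Direction is also open. One would expect earlier stretching of visits to lengthen the recorded time. If reaching weekly visits triggers the endpoint, earlier stretching shortens it instead. Interval censoring does not cure that; only reconciling the endpoint text does.

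A reader might further infer that similar stretching in both arms hides real differences and so favours equivalence. Step 4 shows otherwise: the common delay cancels, and any extra noise would slightly widen the confidence interval and make equivalence harder to show.

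Finally, the rule for dating healing between photographs could sit in an analysis plan not shown, and the protocol never says that dates are exact. That is fair for the dating rule. The protocol does name the test, however, and a comparison of average healing times cannot by itself accommodate an interval or an unhealed wound.

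**Conclusion.** The point holds in a limited form and is a worthwhile refinement rather than a serious flaw. The named tests do not match how healing is observed. The visit-spacing part is small: about 0.75 day if one arm is seen every 2 days and the other every 3.5 days. That raises 5% rejection to 5.4% at an SE of 4.08 days, or to between 5.2% and 8.8% over assumed SDs of 20 down to 5 days. It is essentially zero if spacing is the same in both arms. Figures of 1.2 to 2.5 days apply only if weekly visits precede the healing photograph.

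The lack of a value for unhealed wounds carries more weight. In the illustration it removes over 40% of a true difference (1 − 5.5/9.6 = 43%). That rests on assumed medians and log-SD, and on such wounds being dropped, which the protocol neither states nor rules out.

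Because the equivalence margin has no stated value, the document cannot settle whether shifts of this size would change the conclusion.

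**What to change.** 1. Reconcile the endpoint wording in the Wound Care section (weekly visits, score below 2) with that in Appendix A (one week after complete healing, subscore rule), so that a photograph scored as healed has one meaning. This comes first, because the analysis depends on it.
2. Leave the visit schedule as it is. For each participant, take the date of the last photograph scored not healed and the date of the first scored healed.
3. Replace the t-test and Mann-Whitney for the primary outcome. Treat healing time as interval-censored between those dates, or right-censored at the last photograph if the wound is never scored healed. Compare arms with an interval-censored time-to-event model, for example Weibull, and report the effect with its confidence interval.

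The cost is analysis wording only: photographs are already dated and taken at every dressing change. The drawback is a parametric and slightly less familiar method than a t-test. Right-censoring also assumes that leaving is unrelated to healing. That is doubtful for participants removed for deterioration, so the report should count them by arm.

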It is likely that through coincidence there will be participants who do not have capacity to consent to participate. Potential participants will be screened for cognitive impairment and flagged for additional investigation via a cognitive screening assessment. This study is considered by ACT Legislation as 'low risk research' due to the fact it is comparing the effectiveness of two established standard treatments during routine health care (ACT Health Research Ethics and Governance Office, no date). As a result, if a cognitive impairment is determined then consent will be sought from the potential participant's (in priority order):

- person with enduring power of attorney;
- their guardian; or
- their health attorney, defined as a domestic partner, their carer or a close relative or friend (ACT Health Research Ethics and Governance Office, no date).

This is the most likely vulnerable population to be included in the study.

Adverse Event - Deterioration or development of new pressure injuries

All new pressure injuries and all deteriorating pressure injuries will be referred to the Data Safety and Monitoring Board (DSMB), consisting of Community Care Wound CNC, Community Care Wound Nurse Practitioner and Primary Investigator. This committee will review the circumstance to determine the cause of the deterioration or new pressure injury. If the suspected cause is something external to the mattress then the mattress may be able to remain in place. If no external cause can be found, then it is possible the mattress may have been a factor and the participant may need to leave the trial. This will also be the case should the pressure injury deteriorate to become a Stage 3, Stage 4, Suspected Deep Tissue Injury or Unstageable pressure injury.

Support surface provision during the study

Support surfaces being provided for the study are being supplied by one of two options:

- Equipment suppliers Astris Lifecare and Invacare (mattresses and cushions are being donated for the duration of the study, provided on a needs-basis).
- ACT Health Equipment Loan Service

Which service provides the support surfaces will depend on availability at the time and speed that delivery can occur. Agreements are being drawn up with Astris Lifecare and Invacare with regards to maintaining the privacy of participants and the intellectual property of the results, including the agreement that the results

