will be published, regardless of the outcome. ACT Health equipment will only be utilised for participants who would normally be accessing this equipment, as per current practice.

Support surface provision at the end of the study

As a large number of people with a pressure injury are likely to need pressure care on a long term basis, systems need to be in place to aid the long term provision once the study has completed. At the intake of the study, participants will be receiving an initial occupational therapy assessment which will anticipate any long term equipment needs and refer on appropriately. This initial assessment will be handed over to the treating occupational therapist for follow up at the completion of the study.

Study protocol audits

The DSMB will be responsible for the completion of a quarterly audit to ensure adherence to the protocol is maintained. This will involve checking consent forms have been obtained, photograph documents and assessment documents are saved in the appropriate places and that surveys and mattress provision within the allocated timeframes.

Project Plan

Date	Activity		
Nov 2017 – Jan 2018	HREC Approval sought (ACT Health and UC)		
	Training of Community Nurses for team participating in Pilot		
Feb – Apr 2018	Pilot Study to test methodology		
Apr – Jun 2018	Review results of Pilot Study regarding methodology and data collection – proposed		
	changes to methodology submitted to HREC for approval		
Apr – Jun 2018	Training of Community Nurses for remaining participating teams		
Jul 2018 – Jul 2020	Primary data collection phase – data collection expected to take approx 18-20		
	months with an average of one participants enrolled each week (based on snapshot		
	of potentially eligible participants from Aug-Dec 2016)		
Jul 2020 – Jul 2021	Data analysis		
Jul 2021 -	Writing results, including publications and thesis		

Research Outcomes

Primary Publication	PhD Thesis			
Proposed Journal	Literature review			
Publications	Pilot study			
	Primary RCT focusing primarily on the wound healing component with subjective factors as supportive			
	Article focusing in more detail on the survey results and subjective factors of the mattresses			
Conference Papers	Literature review			
	Results regarding Pilot Study			
	Results regarding Primary RCT			
	would include Occupational Therapy conferences, Wound Care conferences, Nursing Technology conferences			

Budget and Resources Required

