7. Participant provided with Baseline survey and Pain Scale	Primary Researcher

Step	Who
 8. Allocation of support surface Participant allocated to a treatment group using a random-number generator 1=active 2=reactive 	Primary Researcher
9. Provision of support surface (mattress and cushion) TARGET: Participant to be provided with allocated support surface within 2 days to minimise clinical risk of wound deteriorating	Primary Researcher
Participant will be provided with a mattress chosen from the allocated group based on availability. For example if participant is allocated to the 'active' group then they may be provided any of the mattresses listed in that group, based on availability.	
 The following considerations will be made when determining supplier of the allocated mattress: Is the required equipment clinically applicable? In some cases provision of a mattress may not be clinically applicable as a less invasive technique is often trialled first, such as heel elevation when the person has no previous history of pressure injuries. Similarly, not all people would require a cushion for sitting out of bed. In these instances, the allocated equipment will provide an appropriate level of care but may be marginally more intrusive than standard care. Mattress availability from the supplier. 	
 Suppliers of Support Surfaces: a) ACT Health Equipment Loan Service (ELS) – if allocated equipment is available and clinically applicable b) Astris Lifecare – if allocated equipment is not available from ELS or clinically applicable c) Invacare – if allocated equipment is not available from ELS or Astris Lifecare 	Information only
Active mattresses: a) Premium Digital 5 (overlay) – ELS, Invacare b) Premium Digital 9 (replacement) – ELS, Invacare c) Nimbus3 (replacement) – ELS d) Curocell Uno (replacement) – Astris e) Virtuoso (replacement) – Astris f) Salsbury (overlay) – Astris Reactive mattresses:	Information only
 g) ROHO Sections (1x foam and 3x ROHO sections, overlay) – ELS, Astris h) Atmosair (replacement) – ELS i) Softform Premier (replacement) – ELS, Invacare j) Curocell AREA (replacement) – Astris k) Curocell SAM (overlay) – ELS, Astris l) Pressureguard CFT (replacement) – Invacare m) BetterLiving Triple Layer (replacement) - Invacare 	
Cushion: 18"- 20" single valve high profile ROHO – ELS, Astris 10. Referral to be made to the appropriate supplier for provision of support surfaces:	Primary Researcher

Step	Who

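### The Primary Investigator, who by strong inference allocates and arranges the mattress, sits on the three-member board that attributes each deterioration to the mattress or to another cause, and that board also audits the investigator's own tasks

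*Protocol*

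**What the plan says.** **Board and remit.** The Protocol section on adverse events (deterioration or development of new pressure injuries) sets up a Data Safety and Monitoring Board "consisting of Community Care Wound CNC, Community Care Wound Nurse Practitioner and Primary Investigator". Its task is stated directly: "This committee will review the circumstance to determine the cause of the deterioration or new pressure injury". Two outcomes follow. "If the suspected cause is something external to the mattress then the mattress may be able to remain in place". If no external cause is found, "it is possible the mattress may have been a factor and the participant may need to leave the trial". The section extends the leaving provision to any injury that progresses to Stage 3, Stage 4, suspected deep tissue injury or unstageable.

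**Audit.** Under Study protocol audits, "The DSMB will be responsible for the completion of a quarterly audit to ensure adherence to the protocol is maintained". The audit covers consent forms, the filing of photographs and of assessments, and the timeliness of surveys and of mattress provision.

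**Who does the work.** Appendix A assigns consent (step 2), the baseline survey (step 7), allocation (step 8: "Participant allocated to a treatment group using a random-number generator") and provision of the surface (step 9: "Participant to be provided with allocated support surface within 2 days to minimise clinical risk of wound deteriorating") to the Primary Researcher.

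**Exit.** The participant-completion step of Appendix A makes removal from the assigned surface one of the events that end participation.

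**The concern.** Deciding whether a wound worsened because of the mattress or for some other reason is a judgement, and here it can decide whether a participant stays under observation. One of the three people making it knows the arm, because the same role allocates and arranges the mattress. That person also leads a trial whose Research Question and Design section expects the two mattress types to be equivalent or at least non-inferior. Nothing in the document has that member step aside or keeps the arm out of the review.

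The main analysis compares average healing times. A participant who leaves before healing has no observed healing time and is no longer followed for new injuries or for non-healing at 8 weeks. These exits follow bad outcomes, so a process that treats similar cases differently by arm could make losses uneven in a trial that aims for 30 analysed per group.

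The audit raises a separate question of independence. A quarterly check of consent, survey timing and mattress delivery offers limited assurance if the person responsible for those tasks helps carry it out.

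**Working it through.** The point concerns roles, and the plan gives no figure to reproduce. The check traces each role through the Protocol.

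**Step 1: Are the Primary Investigator and the Primary Researcher the same role?** The document does not say so outright. Two comparisons support it.
- Survey work: Outcome Measures has the primary researcher facilitate the survey, while Data Collection speaks of the primary investigator collecting the survey data.
- Review of new injuries: the adverse-event section gives it to a board that includes the Primary Investigator, while Appendix A step 12 gives it to the Wound Nurse Practitioner and the Primary Researcher.

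The inference is strong, but it remains an inference.

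**Step 2: Does this person know the arm?** Yes, if Appendix A is followed. Step 8 has the Primary Researcher make the allocation, and steps 9 and 10 have the same role arrange the equipment. The Random allocation section of the main text describes sealed envelopes instead, and the two descriptions should be reconciled. Either way, the person arranging a mattress of the assigned type knows the type. The role does not always choose the model: on the supplier route, "Sales Representative to choose mattress from pre-determined list based on mattress type and storeroom availability".

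**Step 3: Which exits can the attribution influence?**

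| Route out of the trial | Depends on the board's view of cause? |
|---|---|
| Healing of the initial injury, or reaching the time limit | No |
| Request, moving away, hospitalisation, death | No |
| Progression to Stage 3, Stage 4, suspected deep tissue injury or unstageable | No, depends on grade |
| New or worsening injury short of that, no external cause found | Yes |

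Only the last row is exposed. The adverse-event section does not name who makes the final decision that a participant leaves; the board is the natural reading.

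**Step 4: How much of the audit is self-audit?**

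| Audited item | Responsible under Appendix A |
|---|---|
| Consent forms obtained | Primary Researcher (step 2) |
| Surveys on time | Primary Researcher (baseline, step 7; follow-up per Outcome Measures) |
| Mattress provided on time | Primary Researcher (step 9) |
| Photographs filed | Mainly nurses |
| Assessments filed | Mainly nurses |

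Three of the five items are the investigator's own tasks.

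**Step 5: Is there a safeguard elsewhere?** Photographs are scored by blinded assessors, which protects the wound scores but not the decision that can end follow-up. Data Collection codes participants partly to limit identification by the primary investigator, but that concerns survey data and cannot mask someone who made the allocation. No recusal, masked review or independent member is described.

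**The case against.** The case for leaving the board as it is has substance. Two of its three members are not the investigator. The trial compares two established treatments and is classed as low-risk research, two ethics committees review it, and publication is promised whatever the result. Final photographs and a skin check are collected at completion, new injuries are an analysed outcome, and both an Intention to Treat and a Per Protocol analysis are run and compared. The gravest deteriorations lead to the leaving provision whatever their cause. All of this stands and limits the consequence. None of it takes the arm-aware judgement out of the remaining cases or makes the audit of the three tasks independent.

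Three stronger readings are tempting, and the documents do not support them.

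- *A reader might infer that the attribution determines who is in the per-protocol set.* The Statistical Analysis section names that analysis without defining its membership, and the attribution is at most one of several routes out.
- *A reader might infer that the arrangement pulls the arms together and so favours equivalence.* That would need attribution to differ by arm in a particular direction, and nothing in the Protocol shows that it would.
- *A reader might estimate the number of referrals from the 17.3% of deteriorating wounds in the evidence table (the trial of the RIK and Nimbus 3 mattresses).* That figure fits only the RIK arm: 13/75 = 17.3%. The nearest whole-number counts for the control arm give 14/83 = 16.9% and 15/83 = 18.1%; for both arms together, 27/158 = 17.1% and 28/158 = 17.7%. It also comes from acute hospital wards, so it does not give a rate for this community trial.

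Masking the two wound clinicians may be incomplete, because Data Management has the assigned mattress recorded in the clinical file. Masking is therefore a secondary measure here; recusal does not depend on it.

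**Conclusion.** The concern holds as a weakness in independence. One of three board members judges cause knowing the arm, in cases where the answer can end participation, and three of the five audited items are that member's own tasks.

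This rests on two readings: that Primary Investigator and Primary Researcher are one role (strong inference), and that the board makes or steers the decision to leave (natural reading, decision maker not named). The exposure is limited to new or worsening injuries short of Stage 3, Stage 4, suspected deep tissue injury or unstageable. Within those cases the attribution can influence who is lost before healing. The number of cases and the direction and size of any bias are unknown, and no effect on the primary result is demonstrated. The change is worth making because it costs little and removes a conflicted judgement from a decision that bears on follow-up.

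**What to change.** 1. In the adverse-event section and in Study protocol audits, make the Primary Investigator a non-voting presenter of cases who takes no part in deciding cause or removal, or in auditing their own tasks. The two existing wound clinicians take these over. State explicitly who makes the removal decision, and that the Primary Investigator and Primary Researcher are the same role if they are.
2. Reconcile Appendix A step 12, which sends new injuries to the Wound Nurse Practitioner and the Primary Researcher and omits the CNC, with the revised board.
3. Where feasible, have the two clinicians record the suspected cause from photographs and a coded summary before the arm is disclosed, without delaying any safety action.
4. Give the auditors read access to the allocation and provision records. The secure-folder section of Appendix A restricts the allocation document to the research team and does not list either wound clinician role.
5. State a procedure for disagreement.

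This changes who decides, not the clinical grounds on which a participant stays or leaves. It needs no new staff: the cost is protocol wording, a change in folder permissions and some time from the two clinicians. The Project Plan already schedules submission of methodology changes to the ethics committee after the pilot. The main downside is that two voting members can split on a safety question, so item 5 is needed along with the recusal.
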